3.2.7 Serious Adverse Event

An AE is any untoward medical occurrence in humans, whether or not considered study medication/intervention related which occurs during the conduct of a clinical trial. Any change from baseline in clinical status that is considered clinically significant by the site medical clinician are considered AEs. A suspected adverse reaction is any AE for which there is a reasonable possibility that the study medication/intervention caused the AE. A reasonable possibility implies that there is evidence that the study medication/intervention caused the event. Adverse reaction is any AE caused by the study medication/intervention.

An adverse event, suspected adverse reaction, or adverse reaction is considered serious (i.e., a serious adverse event, serious suspected adverse reaction or serious adverse reaction) if, in the view of either the site medical clinician or sponsor, it:

- Results in death: A death occurring during the study, or which comes to the attention of the study staff during the protocol-defined follow-up period, whether or not considered caused by the study medication/intervention, must be reported.
- Is life-threatening: Life-threatening means that the study participant was, in the opinion of the medical clinician or sponsor, at immediate risk of death from the reaction as it occurred and required immediate intervention.
- Requires inpatient hospitalization or prolongation of existing hospitalization.

- Results in persistent or significant incapacity or substantial disruption of the ability to conduct normal life functions.
- Is a congenital abnormality or birth defect.
- Is an important medical event that may not result in one of the above outcomes but may jeopardize the health of the study participant or require medical or surgical intervention to prevent one of the outcomes listed in the above definition of serious event.

3.3 Table, Figures and Listings Conventions

Data for pre-screened and screened populations will be summarized by site and step. Data for the ITT population will be summarized by induction procedure (SP or RP). Additionally, most analyses for the ITT population will also be summarized by site excluding supportive analysis for primary outcome and key secondary outcomes. Primary outcome will be summarized by site, step and induction procedure (SP or RP). Analyses for the safety population will be summarized by induction procedure (SP or RP). Data audits and data quality (e.g., protocol deviations) will be summarized by site.

Continuous variables will be summarized using the following descriptive statistics: n (non-missing sample size), mean, standard deviation, percentiles (median, 25th and 75th percentiles, maximum and minimum). Categorical variables will be summarized in terms of frequencies and/or percentages.

Any deviations from the above general conventions will be noted in the subsequent sub-sections.

4.0 PARTICIPANT ENROLLMENT, DISPOSITION, AND VISIT ATTENDANCE

4.1 Participant Enrollment

The number of participants pre-screened and screened and the reasons for ineligibility on pre-screening and screening will be summarized by site and step. Note that participants might be pre-screened twice. For participants who were pre-screened twice, they will only be considered for the second screening.

The trajectory of actual enrollment versus the expected number of enrollments according to the start date of each step of the stepped wedge design and based on a monthly expected enrollment rate of 4.675 per site will be graphed by site and overall. Proposed versus actual enrollments will be summarized by site in a tabular fashion. The distribution of enrollments by site, step, and induction procedure will be presented.

4.2 Participant Disposition

Participants are defined as study completers if the Week 8 Post-induction Visit is completed as indicated on the Study Completion (STC) form and are considered early study terminations if this visit is not completed. Participant disposition will be summarized by site and induction procedure for the number of participants completing the study, the number of participants early terminating from the study and the reasons for early study termination.

The CONSORT flow diagram will be generated (Moher et al., 2010).

4.3 Visit Attendance at Post-induction Visits

The number and percentage of participants who attend the post-induction period study visits during Weeks 1 (Day 7), 2 (Day 14), 3 (Day 21), 4 (Day 28), 6 (Day 42), and 8 (Day 56) will be presented by induction procedure and by site. Information on missed visits will also be presented by induction procedure and by site and will include the number of missed visits, the number of participants with at least one missed visit, and the reasons for the missed visits. The expected

number of visits during the post-induction period is calculated based on the general rule that 6 visits are expected per participant who receive the first XR-NTX and two visits (weeks 4 and 8) are expected for participants who fail to receive the first XR-NTX while on the unit during the induction period. The average number of missed visits per participant will be calculated by dividing the number of missed visits by the number of participants. For early study terminations, visits are only considered missed during active study participation if they occur before the study termination date.

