¹Percentages were calculated with the denominator as the number of expected visits at both post-induction Day 28 and Day 56 visits.

Table 14: Summary of Missed Visits by Site

	Gibson Recovery Center (N=XX)	Nexus Recovery Center (N=XX)	Stony Brook Eastern Long Island Hospital (N=XX)	Aspire Health Partners (N=XX)	Avery Road Treatment Center (N=XX)	ADAPT (N=XX)	Total (N=XX)
Number of expected visits ¹	N						
Number of missed visits ²	N (X.x%)						
Number of participants with at least one missed visit ³	N (X.x%)						
Average number of missed visits per participant ⁴	X.x						
Reason for missed visit ⁵							
Participant on vacation	N (X.x%)						
Participant illness							
Participant in hospital, in-patient, or residential treatment							
Participant moved from the area							
Participant incarcerated							
Site closed							
Participant withdrew consent							
Participant deceased							
Participant unable to attend visit due to logistical barriers							
Participant failed to return to site and unable to contact							
Visit was not scheduled							
Unable to contact							
Site decision/error							
COVID-19: Illness							
COVID-19: Public health measures							
COVID-19: Other							
Other							
Unknown							

¹ Expected visits include post-induction Day 28 and Day 56 visits.

² Percentages were calculated based on the denominator of number of expected visits.

³ Percentages were calculated based on the denominator of total number of participants.

⁴ Average number of missed visits per participant with at least one missed visit. The maximum number of missed visits possible was 2 visits.

⁵ Percentages were calculated based on the denominator of number of missed visits.

Table 15: Summary of Missed Visits by Induction Procedure

	Induction Procedure		
	Standard (N=XX)	Rapid (N=XX)	Total (N=XX)
Number of expected visits ¹	N		
Number of missed visits ²	N (X.x%)		
Number of participants with at least one missed visit ³	N (X.x%)		
Average number of missed visits per participant ⁴	X.x		
Reason for missed visit ⁵			
Participant on vacation	N (X.x%)		
Participant illness			
Participant in hospital, in-patient, or residential treatment			
Participant moved from the area			
Participant incarcerated			
Site closed			
Participant withdrew consent			
Participant deceased			
Participant unable to attend visit due to logistical barriers			
Participant failed to return to site and unable to contact			
Visit was not scheduled			
Unable to contact			

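### Read literally, the missed-visit percentage in SAP 4.3 drops post-termination visits from the numerator only, and the table shells use a different visit set and a different average from the text

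*SAP*

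**What the plan says.** SAP 4.3 (Visit Attendance at Post-induction Visits) promises attendance by induction procedure and by site at Weeks 1, 2, 3, 4, 6 and 8. It then gives three rules for missed visits:

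- **Expected visits.** The count "is calculated based on the general rule that 6 visits are expected per participant" who receives the first injection, and two (Weeks 4 and 8) for an induction failure. No exception for early termination is written.
- **Missed visits.** For early terminations, "visits are only considered missed during active study participation if they occur before the study termination date".
- **Average.** "The average number of missed visits per participant will be calculated by dividing the number of missed visits by the number of participants".

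SAP 4.2 makes early termination a broad category. Participants "are considered early study terminations if this visit is not completed", meaning the Week 8 visit.

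The shells in SAP 19.1.1 concerned are Tables 12 and 13 (post-induction attendance by site and by induction procedure) and Tables 14 and 15 (missed visits by site and by induction procedure). Some table numbers repeat in that appendix, so the titles matter. Tables 12 and 13 have rows for Day 28 and Day 56 only. In Tables 14 and 15 the missed-visit percentage has expected visits as its denominator, and the footnotes read "Expected visits include post-induction Day 28 and Day 56 visits" and "Average number of missed visits per participant with at least one missed visit. The maximum number of missed visits possible was 2 visits".

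**The concern.** A percentage of missed visits is interpretable when its numerator and denominator cover the same visits. Here a visit scheduled after termination cannot be counted as missed, yet nothing takes it out of the expected count. Each early termination then adds visits that can only lower the percentage, so an arm that loses more people can look as if it misses fewer visits.

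The text and the shells also describe different tables. A programmer following 4.3 would tabulate up to six visits per inducted participant and average over everyone. One following the shells would tabulate two visits and average only over those who missed one.

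At stake is how follow-up is described by arm for post-induction outcomes such as overdose self-report and, in the inducted population, opioid use, craving and withdrawal. Protocol 16.9 expects missed visits and dropout for outcomes other than the primary and assumes that those data are missing at random. SAP 8.7 addresses missing data for the primary outcome only. The visit tables are therefore one of the few planned views of post-induction missingness, and as drafted no shell shows Weeks 1, 2, 3 or 6.

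**Working it through.** The plan states no missed-visit percentage, so there is no figure to reproduce. The visit counts, planned sample size and success rates below come from the documents. The missed-visit rates, termination rates and termination times are assumptions.

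**Formulas.** Let E be expected visits, L the visits scheduled after termination, and m the missed rate while still in the study.

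- As written: m(E − L)/E
- Matched visits: m(E − L)/(E − L) = m
- All non-attendance: [m(E − L) + L]/E

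The as-written figure is m multiplied by (E − L)/E, so it falls as L grows.

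**Simple example.** Take 100 inducted participants, so E = 100 × 6 = 600. Assume 30 attend Weeks 1 and 2 and then terminate, so L = 30 × 4 = 120. Assume the other 70 miss 10% of their visits: 70 × 6 × 0.10 = 42.

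- As written: 42/600 = 7.0%
- Matched visits: 42/(600 − 120) = 42/480 = 8.75%
- All non-attendance: (42 + 120)/600 = 27%

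The ratio error is the gap between 7.0% and 8.75%. The 27% is a different quantity.

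**By arm, on the shell visit set.** Protocol 8.0 plans about 225 participants per procedure, so E = 225 × 2 = 450. Assume m = 10% and termination before Day 28.

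| Early termination | L | Missed | As written | Matched | All non-attendance |
|---|---|---|---|---|---|
| 20% | 90 | 36 | 36/450 = 8.0% | 36/360 = 10.0% | 126/450 = 28.0% |
| 40% | 180 | 27 | 27/450 = 6.0% | 27/270 = 10.0% | 207/450 = 46.0% |

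If SP had 20% termination and RP 40%, the missed-visit table would print 8.0% against 6.0%, although the active-time rate is the same. With m = 5% the pair is 4.0% and 3.0%; with m = 20% it is 16.0% and 12.0%.

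**By arm, on the 4.3 visit set.** With the SAP 12.0 success rates of 0.55 and 0.70:

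- SP: E = 225 × (0.55 × 6 + 0.45 × 2) = 945
- RP: E = 225 × (0.70 × 6 + 0.30 × 2) = 1080

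Assume inducted participants who terminate do so after Week 3 (3 visits lost) and failures before Week 4 (2 lost). With m = 10%, the as-written figure is 8.8% (SP) and 8.9% (RP) at 20% termination, and 7.6% and 7.8% at 40%. The matched figure is 10.0% throughout.

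**The average.** On the shell visit set, with m = 10%, 20% termination and independent visits, 36 visits are missed. The 4.3 average is 36/225 = 0.16. Participants with at least one missed visit number 180 × (1 − 0.9²) = 34.2, so the shell average is 36/34.2 = 1.05. At 40% termination the two are 27/225 = 0.12 and 27/25.65 = 1.05.

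**The maximum.** Under 4.3 an inducted participant can miss six visits; the shell footnote says two.

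**The case against.** A reader might infer that the plan understates or hides missing follow-up in general. The documents do not support that, for these reasons:

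- **The denominator rests on silence.** SAP 4.3 calls the six/two count a general rule and then adds a sentence for early terminations. It never says that post-termination visits stay in the expected count, and programming could remove them. The point therefore holds for the literal reading.
- **Departures are reported elsewhere.** Tables 12 and 13 give attendance over expected Day 28 and Day 56 visits, and the complement is total non-attendance at those visits. The disposition tables give early terminations and reasons by procedure, and a CONSORT diagram is planned. The 27% in the example is thus not the size of the error.
- **The discrepancies do not all point one way.** The shell average is larger than the 4.3 average. Limiting the table to Day 28 and Day 56 can move the percentage in either direction.
- **The main analyses are untouched.** The primary outcome expects no missing data, the key secondary craving, COWS and SOWS analyses use daily induction-phase data, and no model uses the missed-visit percentage.

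There is also a case for the shells. Day 28 and Day 56 are the only visits scheduled for every enrolled participant. Pooling six-visit and two-visit schedules makes the visit mix depend on each arm's success rate (945 against 1080 expected visits above). That argues for reporting per visit, and the fix follows it.

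What remains is the mismatch on the literal reading, and two contradictions between text and shells that need no inference. The missed-visit reasons in Tables 14 and 15 add to the uncertainty: they include death and withdrawal of consent, so it is unclear which visits after departure count. Under SAP 4.2, a missed Week 8 visit counts only if the recorded termination date falls after it.

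**Conclusion.** The point holds for the descriptive post-induction tables. Read literally, the missed-visit percentage is the active-time rate shrunk by the share of expected visits that fell before termination. The shrinkage is greater in the arm with more termination: 7.0% against 8.75% in the simple example, and 8.0% against 6.0% between arms whose matched rate is 10.0% in both. These sizes depend on assumed missed-visit and termination rates, and on an expected count that is not truncated at termination.

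The shells also contradict SAP 4.3 on the visit set and on the average whichever reading is taken. None of this reaches the primary non-inferiority test or the induction-phase key secondary analyses, and total Day 28 and Day 56 non-attendance can already be derived. It is still worth correcting, because the by-arm numbers would otherwise depend on which part of the SAP the programmer follows.

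**What to change.** 1. In SAP 4.3 and Tables 14 and 15, divide visits missed while active by visits due before termination, and say so explicitly. Leave total non-attendance to the attendance tables, with all scheduled visits as the denominator.
2. In Tables 12 and 13, add Weeks 1, 2, 3 and 6 for inducted participants, as 4.3 states. Report them per visit, and keep Day 28 and Day 56 as the summary common to all participants, so that pooling two schedules does not make the arms less comparable. Correct the stated maximum of two missed visits wherever the six-visit schedule applies.
3. Use one average throughout: missed visits divided by all participants, as in 4.3.

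The cost is a wording change in 4.3, revised footnotes and a few extra table rows. No new data are needed.

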5.0 ANALYSIS OF PARTICIPANT BASELINE CHARACTERISTICS

Baseline demographics and characteristics including sex (at birth) (DEM), age, ethnicity, race, education level, marital status, and employment will be summarized by site and induction procedure for the ITT population. The following additional important baseline characteristics will also be summarized by site and induction procedure: gender and sexual orientation (S97), homelessness status (NMS), first COWS score recorded on Day 1 of admission (COW), history of overdose (ODQ), number of days since last self-reported opioid use at Day 1 of admission (TAP), baseline substance use (UDS and TLFB), medical and psychiatric history (MHX), baseline mental health screening: Adult ADHD Self-Report Screening Scale for DSM-5 (Score \geq 14) (AAS), PTSD Checklist for DSM-5 (Score \geq 31) (PCL), Generalized Anxiety Disorder (Score \geq 8) (GA7), Patient Health Questionnaire (PHQ-9) (Score \geq 10), criminal history (NMS), health insurance/care plan (NMS), history of medication for opioid use disorder (NMS), number of times attempted and completed opioid detoxification (MHX) and previous unsuccessful inductions onto XR-NTX (MHX). Age will be summarized as a continuous and categorial variable. A summary of baseline demographics and characteristics will also be presented for study completers. If differences between induction procedures are suspected, statistical testing may be performed.

6.0 MEDICATIONS ADMINISTERED DURING INDUCTION PHASE

The daily medications for an enrolled participant for each day of the induction phase are reported on the Daily Medication Log (DMA) form. These data are abstracted from medical records starting with admission Day 1 and up to the last day of the induction phase. The number of participants with at least one dose of each medication will be summarized by induction procedure. The daily medication log will be summarized for each day of the induction phase by induction procedure. Medications administered in the Standard Procedure will be summarized by Buprenorphine Day, Buprenorphine Washout Day, Naltrexone Day, Day of XR-NTX Injection Success or Day of XR-NTX Injection Failure. Medications administered in the Rapid Procedure will be summarized by Pre-Buprenorphine Day, Buprenorphine Day, Buprenorphine Washout Day, Naltrexone Day, and Day of XR-NTX Injection Success or Day of XR-NTX Injection Failure.

7.0 TREATMENT EXPOSURE

During the study (induction and post-induction phase), three XR-NTX study injections are expected per participant. First study injection is recorded on the EOI form, and study injections 2 and 3 are recorded on the INN form. The treatment exposure percentage is calculated as the number of injections administered divided by the number of injections expected. Regardless of induction procedure, participants are expected to receive the first XR-NTX injection within 30 days maximum from admission, and second and third XR-NTX injections at Day 28 and at Day 56 post first injection, respectively. Treatment exposure will be summarized by site and by induction procedure. Note that a study injection is defined as any XR-NTX injection given from the CTN-0097 study supply or from CTN-0100 supply for cross-over participants. Any XR-NTX injection received outside of the CTN-0097 or CTN-0100 supply is not considered study injection, and is recorded on the Timeline Followback Medications (M97) form. XR-NTX injections received by

participants who failed their initial induction while on the but later received an injection during the post-induction period are recorded on the M97 form and will be summarized by site and original induction procedure separately.

8.0 EFFECTIVENESS ANALYSIS

8.1 Definition of the Primary Outcome Measure

The primary outcome measure is the proportion of participants who receive the first XR-NTX injection (dichotomous: participant did or did not receive first injection of XR-NTX) while on the treatment unit within 30 days of admission. The primary objective of the study is to show RP is non-inferior to SP XR-NTX induction method. The hypothesis is that RP will be non-inferior to SP in terms of proportion of participants with successful inductions (receipt of first XR-NTX injection) while on the unit. The primary outcome will be determined from the EOI form using the EINTXIND variable for Segment C and D.

8.2 Analysis of the Primary Outcome Measure

A summary of the number of participants who receive their first injection will be presented by site, by step and by induction procedure. The main analyses for the primary outcome will use the ITT population. As is standard for the analysis of stepped-wedge designs (Barker et al., 2016; Hussey and Hughes, 2007), the primary outcome analysis for non-inferiority will be performed using a generalized linear mixed-effects model with a logistic link. The log odds of a participant receiving the first XR-NTX injection (yes/no) will be modeled as a function of which induction procedure (RP vs SP), step 1 through 5 (to control for secular trends), and a random effect for site to control for nesting of participants within site. The null hypothesis of inferiority of RP to SP will be rejected if the lower 95% confidence limit of the odds ratio of success [odds(RP)/odds(SP)] exceeds 0.67. If null hypothesis of inferiority of RP to SP is rejected, then superiority of RP will be tested. If the 95% confidence interval for the odds ratio is above 0.67 and is also above 1, then there will be evidence of superiority and it is acceptable to calculate the p-value (CPMP, 2001). The covariance structure compound symmetry (CS, correlations over time are constant) will be used for the observations from a particular site. Other correlation structures will be examined (Hemming et al., 2017). The best model will be selected based on the lowest Bayesian Information Criterion (BIC). The Satterthwaite method to adjust for denominator degrees of freedom for tests of the fixed effects will be used.

Logistic model will be used:

$$\begin{aligned} \text{logit}(p_{ijs}) &= J_{js} * \delta + \theta_s + \alpha_j \\ \alpha_j &\sim N(0, \tau^2) \end{aligned}$$

Alternative logistic model with autoregressive lag-1(AR(1)) correlation structure:

$$\begin{aligned} \text{logit}(p_{ijs}) &= J_{js} * \delta + \theta_s + \alpha_{js} \\ \alpha_{js} &\sim N(0, \tau^2) \\ \text{Cov}(\alpha_{js}, \alpha_{jt}) &= \tau^2 \rho^{|t-s|} \end{aligned}$$

where:

- j indexes the site
- s indexes the step
- i indexes the individual within site j at time s
- θ_s is the fixed effect of time

- α_j is the random site effect
- p_{ijs} is the probability of success for individual i within site j at time s
- J_{js} is the treatment indicator for site j at time s
- δ is the treatment effect
- t and s index two different steps (in AR(1) model)

SAS code example:

```
proc glimmix data = primout method = quad IC = PQ;  
  class site trt (ref='SP') step (ref='1');  
  model success (event='1') = trt step / dist = binary link = logit solution oddsratio;  
  random intercept / subject = site;  
run;
```

SAS code example AR(1):

```
proc glimmix data = primout method = quad IC=PQ;  
  class site trt(ref='SP') step (ref='1');  
  model success (event='1')= trt step / dist = binary link = logit solution oddsratio;  
  random step / subject=site type=ar(1);  
run;
```

where:

- success - is the XR-NTX injection status (Yes=1 or No=0)
- trt - is the variable that defines the induction procedure (RP or SP)
- step - is 1 through 5
- site - is the site code for the 6 sites.

The Number Needed to Treat (NNT) will be calculated as the inverse of the absolute difference in rates of success i.e., $1 / (\text{rate of success in RP} - \text{rate of success in SP})$.

